9.3.2.1.2. Drug utilization patterns

Based on the above exposure definitions, the following variables will be derived for the drug utilization patterns:

- Index drug therapy: substance and class of anticoagulant drug therapy, duration of use, dosing, route of administration
- Maintenance therapy: substance and class of anticoagulant drug therapy, duration of use, dosing, route of administration
- Switching to other anticoagulant therapy
- Number and sequence of successive anticoagulation agents during an anticoagulant treatment period.

Operational definition for maintenance therapy and other study variables will be provided in the statistical analysis plan.

9.3.2.1.3. Safety outcomes

Potential cases will be identified using diagnostic codes according to the different coding systems in the data sources (preliminary list in [Annex 3](#)). The severity of bleeding might be difficult to determine accurately in secondary health data sources. However, to estimate the severity of bleeding to the extent possible, two co-primary bleeding outcomes with different severity grading will be assessed: Major bleeding or CRNM bleeding. The definitions for major bleeding and CRNM bleeding are based on prior definitions from the International Society on Thrombosis and Haemostasis (ISTH) and definitions used in the EINSTEIN Junior study, with further adaptation to take into account the availability of information in the data sources (6-8). Besides, the definitions for major bleeding and CRNM bleeding will be mutually exclusive.

Major bleeding

Defined as a hospitalization with one of the following primary, related or associated diagnoses:

- Intracranial haemorrhage
- Other critical organ or site bleeding (intrapinal, intraocular, retroperitoneal, intra-articular or pericardial, or intramuscular with compartment syndrome)
- Gastrointestinal bleeding
- Urogenital bleeding

- Other bleeding with a transfusion during hospital stay or resulting in death.

A secondary analysis will be based on an analysis per bleeding site (as described above), if numbers permit.

Clinically Relevant Non-Major (CRNM) bleeding

Defined as bleeding not meeting the criteria for major bleeding, but reported as a primary, related or associated diagnosis during hospitalization.

A sensitivity analysis is planned for major and CRNM bleeding with a more restrictive definition using only main/primary diagnostic codes, excluding secondary diagnostic codes.

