Then, for each data source and population (i.e., overall study population and subgroup of patients with rivaroxaban oral suspension), the lowest, highest, and average number of expected outcomes were estimated by using the incidence rates of the pivotal Phase III EINSTEIN Junior study as reference for the CRNM bleeding (5.6% with rivaroxaban, 5.9% with comparator) and the VTE events (1.2% with rivaroxaban, 3.0% with comparator).

Over 2021-2026, an average of 650 children under two years with VTE would be identified in the SNDS (range from 242 to 1058), with an average of 219 of them (range 81-356) using rivaroxaban oral suspension, and an average of 12 of them (range 5-20) having a bleeding with hospitalization. In the Swedish national registers, this would lead to an average total of 98 children under two years with VTE (range 37-160), with 33 of them receiving rivaroxaban oral suspension (range 12-54), and 2 of them with a bleeding with hospitalization (range 1-3). In the Danish national registers, an average total of 52 children under two years with VTE (range 19-85) is expected, with 18 of them receiving rivaroxaban oral suspension (range 7-29), and 1 of them with a bleeding with hospitalization (range 0-2). In SIDIAP, we could expect an average total of 45 children under two

years with VTE (range 17-73), with 15 of them receiving rivaroxaban oral suspension (range 6-25), and 1 of them with a bleeding with hospitalization (range 0-1).

Based on these patient count estimations, the expected total study size in the four target countries (Denmark, France, Spain, and Sweden) is about 850 children under two years with VTE, with approximately 280 of them using rivaroxaban oral suspension.

Of note, small cell counts must be suppressed in results from all data sources to mitigate the risk of re-identification. Due to the small sample size and low frequency of the outcomes, it is expected that the outcomes analysis with respect to bleedings and recurrent VTE should only be feasible in the SNDS (as shown in [Table 6](#)).

Table 6: Estimation of patient counts

Country - Data source(s)	Denmark national registers	France SNDS	Spain SIDIAP	Sweden national registers	Overall
Children <2y with VTE^a					
Annual number					
Lowest estimate	3	40	3	6	52
Highest estimate	14	176	12	27	229
Average estimate	9	108	7	16	141
Cumulative number of patients over 2021-2026					
Lowest estimate	19	242	17	37	315
Highest estimate	85	1058	73	160	1376

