Average estimate	52	650	45	98	846
Cumulative number of outcomes over 2021-2026^b					
Bleeding with hosp. - Lowest estimate	1	14	1	2	18
Bleeding with hosp. - Highest estimate	5	61	4	9	79
Bleeding with hosp. - Average estimate	3	37	3	6	49
Recurrent VTE - Lowest estimate	0	5	0	1	7
Recurrent VTE - Highest estimate	2	22	2	3	29
Recurrent VTE - Average estimate	1	14	1	2	18
Children <2y with VTE and receiving rivaroxaban granules for oral suspension^c					
Cumulative number of patients over 2021-2026					
Lowest estimate	7	81	6	12	106
Highest estimate	29	356	25	54	463
Average estimate	18	219	15	33	285
Cumulative number of outcomes over 2021-2026^b					
Bleeding with hosp. - Lowest estimate	0	5	0	1	6
Bleeding with hosp. - Highest estimate	2	20	1	3	26
Bleeding with hosp. - Average estimate	1	12	1	2	16
Recurrent VTE - Lowest estimate	0	1	0	0	1
Recurrent VTE - Highest estimate	0	4	0	1	6
Recurrent VTE - Average estimate	0	3	0	0	3

CRNM = Clinically relevant non-major; SIDIAP = Sistema d'Informació per al Desenvolupament de l'Investigació en Atenció Primària; SNDS = Système National Des Données De Santé; VTE = Venous thromboembolism

Counts in red are below disclosure threshold.

^a Lowest estimate based on incidence rate of VTE of 0.14/10,000 and 20% of children under two years among children with VTE. Highest estimate based on incidence rate of VTE of 0.49/10,000 and 25% of children under two years among children with VTE. Average estimate is the mean of lowest and highest estimates.

^b Based on respective estimate of patients' number and outcome incidence from EINSTEIN JR: 5.6% (rivaroxaban) and 5.9% (comparator) for bleeding with hospitalization (major + CRNM bleedings); 1.2% (rivaroxaban) and 3.0% (comparator) for recurrent VTE.

^c Based on market share scenario for rivaroxaban oral suspension: 10% in 2021, 32% in 2022, 38% in 2023, 42% in 2024, 50% in 2025 and 30% in 2026.

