9.7.4. Safety and effectiveness outcomes

Analyses of outcomes will be conducted according to anticoagulation therapy received: rivaroxaban and SOC (including heparins, VKAs, and other DOACs).

Time at risk will consider the exposure of interest (rivaroxaban or SOC) according to the as-treated assumption. For each outcome, the first occurrence for that outcome during time at risk will be identified.

The primary analysis of major bleeding will be based on the outcome definition considering all bleedings at critical sites (or requiring transfusion or resulting in death). A secondary analysis will be based on an analysis per bleeding site if numbers permit.

For each exposure category:

- A crude incidence rate with corresponding 95% CI will be estimated for each outcome.
- The cumulative incidence with 95% CI of each outcome will be estimated at regular time intervals (e.g., at 3, 6, 9 and 12 months).
- Event-free survival of each outcome will be presented graphically with the Kaplan-Meier method.

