9.7.7. Subgroup analysis

A subgroup analysis for primary and secondary outcomes will be performed by age of children at index date (<6 months and 6 months to <2 years).

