9.7.8. Combined analysis across data sources

In addition to separate analysis in each data source, descriptive analyses combining cumulative aggregated data of each individual data source will be conducted when possible.

According to GDPR, values must be suppressed whenever a patient count is less than a defined threshold: less than five cases/observations in the Nordic countries, less than six in Spain, and less than ten in France.

Therefore, combined analyses should be possible for characteristics of patients and drug use patterns. However, due to the small sample size and rarity of the outcomes bleedings and recurrent VTE, it is expected that these analyses should only be feasible in the SNDS, in which case combined analyses of outcomes across data sources would not be possible.

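### SNDS is rated feasible for the bleeding objective on major and CRNM bleeding combined, but only the two separate outcomes are planned, and on rivaroxaban at least one is expected below the French disclosure limit

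*Protocol*

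**What the plan says.** Section 9.3.2.1.3 plans that "two co-primary bleeding outcomes with different severity grading will be assessed: Major bleeding or CRNM bleeding" and makes the two definitions mutually exclusive. Section 9.7.4 estimates an incidence rate and a cumulative incidence for each outcome within each exposure category. No section defines or analyses major and CRNM bleeding together.

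The expected counts are built differently. Section 9.5.2 expects for SNDS, among the children with VTE, "with an average of 219 of them (range 81-356) using rivaroxaban oral suspension, and an average of 12 of them (range 5-20) having a bleeding". Table 6 footnote b says the rates behind this count are "for bleeding with hospitalization (major + CRNM bleedings". No expected count is given for either outcome alone.

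Section 9.7.8 sets the suppression limits at "less than five cases/observations in the Nordic countries, less than six in Spain, and less than ten in France". Table 4 marks a data source below threshold when the average expected number of outcomes is under the limit. On that rule SNDS alone is rated feasible for the bleeding objective, and Sections 9.5.2, 9.7.8 and 9.9 rely on SNDS for the outcome analyses. Section 9.7.7 adds: "A subgroup analysis for primary and secondary outcomes will be performed by age of children at index date".

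**The concern.** The quantity tested against the disclosure limit is not one that the study will report. A combined count of 12 clears a limit of ten; the two cells into which it must be divided cannot both do so. The regulator asked for this study because bleeding data in the youngest children are sparse. SNDS is the only source rated able to report bleeding, and Section 9.7.8 expects no combined outcome analysis across sources if only SNDS is feasible. If a rivaroxaban cell is suppressed in SNDS, the plan has no other route to that result. The limitations in Section 9.9 acknowledge suppression elsewhere but exempt SNDS.

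**Working it through.** **Inputs.** SNDS children: 650 on average (242-1058), Section 9.5.2. Market shares: 10, 32, 38, 42, 50 and 30%, Table 6 footnote c. Bleeding proportion on rivaroxaban: 5.6%, footnote b. Origin of that proportion: 2 of 36 children under two (21 + 15), both CRNM, Section 7.2. French limit: counts below ten, Section 9.7.8. The split between major and CRNM is not documented and is varied below.

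**Reproducing the protocol's figure.** Mean share = (10 + 32 + 38 + 42 + 50 + 30)/6 = 33.67%. Patients: 650 × 0.3367 = 218.8 (stated 219). Bleeds: 219 × 0.056 = 12.26 (stated 12). At the lowest estimate, 81 × 0.056 = 4.5 (stated 5); at the highest, 356 × 0.056 = 19.9 (stated 20). All agree.

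**Level at which the rule is applied.** In Table 6 the SNDS average for recurrent VTE is 14 overall and 3 on rivaroxaban, yet Table 4 rates it below threshold. The rating therefore appears to follow the rivaroxaban count, so 12 against ten is the relevant comparison for bleeding.

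**Expected counts after the split.** With major share s, the expected counts are 12.26s and 12.26(1 − s). Two counts of ten need 20, so at least one is below ten for every s. One of them reaches ten only if its share is at least 10/12.26 = 82%.

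**Probability of reaching ten.** Assume a Poisson total with each bleed classified independently and each child counted once. The two counts are then independent Poisson variables, and P(both) is the product of the two tails. The table is symmetric in the two outcomes.

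| Smaller : larger share | Expected counts | P(smaller ≥10) | P(larger ≥10) | P(both) | P(at least one) |
|---|---|---|---|---|---|
| 0:100 | 0 / 12.3 | 0 | 0.78 | 0 | 0.78 |
| 20:80 | 2.5 / 9.8 | <0.001 | 0.52 | <0.001 | 0.52 |
| 30:70 | 3.7 / 8.6 | 0.005 | 0.36 | 0.002 | 0.36 |
| 50:50 | 6.1 / 6.1 | 0.09 | 0.09 | 0.009 | 0.18 |

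At the highest estimate (19.9 bleeds), P(both) peaks at 0.29 at 50:50, and P(at least one) runs from 0.79 to 0.99. At the lowest (4.5 bleeds), even the combined count reaches ten with probability of only 0.02. Binomial tails change these figures by about 0.01 at most.

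**Age subgroups.** Take the most favourable split (all CRNM) and the trial's age mix, 15/36 under six months and 21/36 older. At the average estimate the expected counts are 12.26 × 15/36 = 5.1 and 12.26 × 21/36 = 7.2, with probabilities of about 4% and 19% of reaching ten. At the highest estimate they are about 32% and 72%.

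**Uncertainty of the rate.** The exact (Clopper-Pearson) 95% interval for 2/36 is 0.7% to 18.7%. Over 219 children that is about 1.5 to 41 events. The stated 5-20 varies only the number of patients.

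**The case against.** The strongest reply is that the trial supports a lopsided split. Section 7.2 reports that all ten rivaroxaban bleeds in the trial were CRNM. If that carries over, CRNM bleeding has about a 78% chance of being reportable and only major bleeding is lost, perhaps as a true zero that local rules might let through. This stands, and it rules out the tempting inference that rivaroxaban bleeding results will mostly be suppressed whatever happens: the 50:50 split is an assumption, and at the highest estimate at least one outcome is usually reportable. The lopsided split is not assured either, because Section 9.3.2.1.3 classes any hospital-coded gastrointestinal or urogenital bleed as major.

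For the same reason, a reader should not conclude that the 5.6% is wrongly labelled as major plus CRNM. With no major bleeds on rivaroxaban, 2/36 is numerically both rates. What the documents do not support is treating it as a rate of hospitalised bleeding.

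Rate uncertainty also cuts both ways. At 41 events, both outcomes would reach ten with about 99% probability at 50:50 and 78% at 30:70.

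A reader might infer that every age subgroup will be suppressed. That is likely at the average estimate, but the 72% figure for the older group shows it does not hold over the stated range.

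A reader might also see two rival definitions of major bleeding, since Section 9.7.4 speaks of "considering all bleedings at critical sites (or requiring transfusion or resulting in death" while Section 9.3.2.1.3 lists gastrointestinal and urogenital bleeding without those conditions. Section 9.7.4 refers to the outcome definition and paraphrases it, and Section 9.9 describes major bleeding in line with the list. This is loose wording, not a second definition.

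Finally, the study is descriptive, accrual is monitored yearly and data sources may be added. These points soften the consequence but do not make the Table 4 entry correct.

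**Conclusion.** The point holds for the rivaroxaban group in SNDS. By Table 4's own rule, the unqualified feasibility rating is supported only for a combined outcome that the protocol does not plan. The statement about expected counts needs no assumption on the split; the probabilities rest on the 5.6% rate, the Poisson model and the split shown. Standard of care is less affected: (650 − 219) × 5.9% = 25.4 expected bleeds, so at least one outcome should normally be reportable there. A combined outcome would raise the chance of a reportable rivaroxaban result to about 78% whatever the split, a gain of up to 60 percentage points over the present plan, and of nothing if all bleeds are CRNM. It does not rescue the lowest estimate.

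**What to change.** 1. In Sections 9.3.2.1.3 and 9.7.4, add any hospitalised bleeding (major or CRNM, first event) as a prespecified outcome beside the two co-primaries. Keep both co-primaries and report each where local disclosure rules allow. Requiring both to clear the limit before either is shown would withhold a CRNM result that may be reportable, and would weaken the severity objective.
2. State in advance how a suppressed component will be protected from recovery by subtracting the other from the combined count.
3. In Table 4 and Section 9.5.2, say that the SNDS rating applies to the combined outcome, and that at least one co-primary and the age subgroups are expected below threshold on rivaroxaban at the average estimate.
4. In Section 9.5.2, state that the 5-20 range excludes uncertainty in the 5.6% (2/36, exact 95% interval 0.7-18.7%, about 1.5-41 events in 219 children), and that this was not a rate of hospitalised bleeding.
5. Align the description of major bleeding in Section 9.7.4 with the list in Section 9.3.2.1.3. No extra sensitivity analysis is needed.

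The cost is a change of protocol and SAP wording and one derived variable. The small downside is that the combined outcome mixes severities.

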9.2.3.2. Exclusion criteria

Participants are excluded from the study if any of the following criteria apply:

- None.

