9.3.2. Outcomes

9.3.2.1. Primary outcomes

9.3.2.1.1. Patient characteristics

The following patient characteristics, including risk factors for VTE will be considered:

- Demographic characteristics of patients: age, sex; bodyweight at index date and gestational age, if available
- Characteristics of index VTE, if available (depending on the granularity of codes):
 - Type of location of VTE
 - Central venous catheter related thrombosis
 - Symptomatic versus asymptomatic VTE
- Co-morbidities reported in the previous six months before index date, or since date of birth for children less than six months:
 - Major organ disease (cardiac, gastrointestinal, renal, neurological)
 - Malignancy (active cancer, haematological cancer, solid tumour)
 - Thrombophilia (congenital or acquired), including antithrombin, protein C or Protein S deficiency, factor V Leiden or prothrombin mutation
 - Major surgery or trauma
 - Major infectious disease
 - Major congenital venous anomaly
 - Use of central venous catheter
 - Morbid obesity
 - Hypertension
- Prior treatments reported in the previous six months before index date (or since date of birth for children less than six months): all drugs by third or fourth ATC level
- Comedication during follow-up: all drugs by third or fourth ATC level, and subgroup of all drugs that can increase the risk of bleeding, such as non-steroidal anti-inflammatory drugs, antiplatelets and aspirin
- Health resource utilization in the previous six months before index date (or since date of birth for children less than six months), e.g., marker of health status of the patients, including

- Outpatient visits
- Hospital admissions
- Length of hospital stay
- Admission to intensive care unit
- Duration of oral, nasogastric/gastric feeding before index date (identified via procedure codes), if available

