9.9. Limitations of the research methods

The use of secondary data that has not been primarily collected for research purposes comes with specific limitations.

Selection bias

- All patients fulfilling eligibility criteria will be included in the study. The data sources in the different countries differ in terms of contents and expected coverage. Most have a national coverage, while SIDIAP which only covers ~75% of Catalonia is also considered representative of the Spanish population. Therefore, the selection bias is considered to be low with respect to the target countries.

Information bias

- Exposure data
 - Anticoagulation therapy is expected to be initiated during hospital stay and renewed for outpatient use. According to its indication, rivaroxaban oral suspension should be used after at least five days of initial parenteral anticoagulation treatment. Thus, in theory, all patients receiving rivaroxaban should be switchers from parenteral anticoagulant treatment. In practice, the capacity to observe the actual initial parenteral anticoagulation treatment and its duration will depend on the availability of inpatient drug data in the selected data sources. This will be feasible when

inpatient drug data is captured, e.g., in the Danish SMR (soon available, with data collected since May 2018) and in SIDIAP through linkage with hospital dispensation medication. However, inpatient drug data is not captured in SNDS and in Swedish national registers, which represents a risk of exposure underestimation. In this latter situation, the information on anticoagulation therapy and its duration will be based on outpatient prescriptions only, at a time when patients may have already, or not yet, stopped the initial parenteral anticoagulation treatment, and switched to maintenance therapy like rivaroxaban. Hence, when patients will have switched to rivaroxaban during hospital stay in an unobservable period in the data source, they will appear as initiating anticoagulation therapy with rivaroxaban, and not switchers. To avoid immeasurable time bias, the index date will be the first observed record of anticoagulation therapy in each data source, whether it occurs during inpatient stay or afterwards.

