is also possible that a bleeding occurs while the child is already hospitalized for another reason being reported as the primary diagnosis. To mitigate this risk of misclassification, two definitions will be considered for the bleeding outcomes: in the main analysis, a sensitive approach considering all appropriate bleedings reported as primary, related, or associated diagnoses will be used as the primary definition to capture all bleedings that might represent a major bleeding or a CRNM bleeding. By increasing specificity, a sensitivity analysis restricted to those bleeding events reported as *primary* diagnoses during hospitalization will inform on the robustness of study findings.

- Recurrent symptomatic VTE. Children are likely to come to a specialist/hospital for a control visit or something related to their first VTE. On this occasion they might be recorded with a diagnosis of VTE even if this does not represent a recurrent VTE event. In order to minimize this risk of misclassification, the outcome of recurrent VTE will be restricted to VTE diagnoses recorded in inpatient setting, thus excluding control visits for VTE which most likely occur in secondary outpatient care. However, a risk of misclassification remains for children hospitalized for a long period or for other reasons than the index VTE, where it might be difficult to distinguish a recurrent VTE event from the index VTE. For this reason, the use of a primary definition of VTE diagnoses, including all primary/main and secondary diagnoses codes, and a secondary more specific definition restricted to primary VTE diagnoses reported through hospitalization will allow to test the robustness of the findings.

Other limitations

- **Impact of the small sample size**

The number of available children aged under two years with VTE is expected to be very low in most data sources due to VTE being a rare event in this population. For this reason, all analyses will be descriptive and no confirmatory comparison between exposure categories will be performed.

To comply with GDPR, cell suppression is required to mitigate the risk of re-identification in most countries. Consequently, this is a major limitation for analyses in most data sources, except SNDS in France. Besides, due to the small sample size and low frequency of the safety and efficacy outcomes, it is expected that these analyses should only be feasible in the SNDS.

- **Missing data**

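### The co-primary bleeding outcomes do not require the bleed to be new, so an earlier bleed coded again at a readmission on treatment counts as an on-drug bleed, and no planned sensitivity analysis isolates this

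*Protocol*

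**What the plan says.** Section 9.3.2.1.3 gives the two co-primary definitions. Major bleeding is "Defined as a hospitalization with one of the following primary, related or associated diagnoses", followed by a list of sites. Clinically relevant non-major bleeding is "Defined as bleeding not meeting the criteria for major bleeding, but reported as a primary, related or associated diagnosis during hospitalization". Annex 3 gives a preliminary code list, whose intracranial group includes the injury codes S064-S068.

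The counting rule is in 9.7.4: "For each outcome, the first occurrence for that outcome during time at risk will be identified". Time at risk starts at the index date, and according to 9.9 "the index date will be the first observed record of anticoagulation therapy in each data source, whether it occurs during inpatient stay or afterwards".

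Section 9.2.3.2 opens with "Participants are excluded from the study if any of the following criteria apply" and then lists none. The baseline conditions in 9.3.2.1.1 include "Major surgery or trauma", but not prior bleeding.

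Section 9.9 explains that the main definition is deliberately broad: "a sensitive approach considering all appropriate bleedings reported as primary, related, or associated diagnoses". The planned counterweight in 9.3.2.1.3 and 9.7.6.2 is one sensitivity analysis restricted to main or primary diagnoses. For recurrent VTE, 9.9 also warns that a later code may only reflect the index event. It gives no such warning for bleeding.

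**The concern.** A diagnosis code on a discharge record shows that a condition was relevant to the stay. It does not show that the condition began during it. With every diagnostic position accepted and no new-event condition, a bleed that happened before anticoagulation becomes an on-treatment outcome once it is coded again in a stay during time at risk.

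This can plausibly occur in this population. Section 7.2 lists trauma among the VTE risk factors, and traumatic intracranial codes are on the outcome list. Take an infant with a traumatic intracranial bleed who then develops VTE, starts rivaroxaban after discharge, and is readmitted with the old code on the record. Read literally, the protocol counts a major bleed on rivaroxaban. Because follow-up for an outcome stops at its first occurrence (9.1, 9.2.2.1), a later true bleed of that kind in the same child would not be counted.

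Bleeding risk is the reason the study was requested (7.1), and few events are expected, so a handful of re-coded bleeds could shift the estimate visibly.

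**Working it through.** **Step 1: what an event must satisfy.** The sections, side by side:

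| Element | Section | New-event condition? |
|---|---|---|
| Major bleeding: listed code, any position, any stay | 9.3.2.1.3 | None |
| Non-major bleeding: other bleeding code, any position | 9.3.2.1.3 | None |
| First occurrence within time at risk | 9.7.4 | First in the window, not first ever |
| Exclusions | 9.2.3.2 | None |
| Baseline conditions | 9.3.2.1.1 | Prior bleeding not listed |
| Primary-diagnosis sensitivity analysis | 9.7.6.2 | Restricts position, not onset |

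A bleeding stay wholly before the index date lies outside time at risk and does not count. Two routes remain:

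- Route A, all sources: an earlier bleed is coded again at a readmission during time at risk.
- Route B, Denmark and SIDIAP: inpatient drug data can place the index date inside a stay, and that stay's record may carry a bleed from before treatment. According to 9.9, SNDS and the Swedish registers do not capture inpatient drugs.

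**Step 2: what the primary-diagnosis analysis does.**

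- Old bleed re-coded in secondary position: removed, as wanted.
- Old bleed as main diagnosis of a readmission: kept, not wanted.
- True new bleed during a stay for another reason, coded as secondary: removed, not wanted.

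A drop in events under that analysis therefore mixes re-codes with genuine bleeds and cannot be read as the size of the re-coding problem.

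**Step 3: reproduce the plan's own figure.** Inputs from 9.5.2 and Table 6: 219 SNDS rivaroxaban users (range 81-356) and 5.6% bleeding incidence.

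- 219 × 0.056 = 12.3 (stated 12)
- 81 × 0.056 = 4.5 (stated 5)
- 356 × 0.056 = 19.9 (stated 20)

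**Step 4: illustration of scale.** Let c be the share of users with an earlier coded bleed and q the chance that it is coded again in a stay during time at risk. The documents give neither, so both are assumptions. The sum also treats re-coded events as falling in children without a counted true bleed.

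Extra events = 219 × c × q; apparent incidence = (12.26 + extra) / 219.

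| c | q | Extra events | Relative to 12.26 | Apparent incidence |
|---|---|---|---|---|
| 2% | 10% | 0.4 | +4% | 5.8% |
| 5% | 20% | 2.2 | +18% | 6.6% |
| 5% | 40% | 4.4 | +36% | 7.6% |

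**Step 5: compare with sampling error.** The exact 95% interval for 12/219 (5.5%) is 2.9-9.4%; for 16/219 (7.3%) it is 4.2-11.6%. Four re-coded events thus move the estimate by 1.8 percentage points, which is within the random uncertainty but always upwards. Raising 12 events by half would take six re-coded bleeds, that is 6/219 = 2.7% of users.

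**The case against.** The strongest reply is that this belongs in the SAP. Sections 9.3.2.1.2 and 9.7.1 leave variable definitions to it, the code list is preliminary, and 9.9 speaks of appropriate bleedings, which leaves room for judgement. An SAP could indeed add a new-event rule. But the protocol itself fixes the co-primary definition, the counting rule and the sensitivity analyses, and does not list this risk among its limitations. What is written admits re-coded bleeds.

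Several stronger inferences are tempting and are not supported:

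- *Neonatal bleeds are swept in.* The preliminary list has no perinatal P-codes, so such bleeds count only if coded under one of the listed codes. Trauma is the example the list supports directly.
- *Bleeds in the index stay distort the reported rates.* Route B concerns Denmark and SIDIAP, each with about one expected rivaroxaban bleed and marked below the disclosure threshold in Table 4. Sections 9.5.2 and 9.7.8 expect outcome analyses only in SNDS, where route B is essentially absent.
- *The planned sensitivity analysis does nothing.* It removes the typical re-code, an old bleed in secondary position.
- *The primary rate is known to be materially inflated, or inflated more in one exposure category.* No input for either statement is in the documents.
- *The main definition should be replaced.* Excluding same-site codes from the main analysis would discard true re-bleeds from a definition chosen for sensitivity. Where the index date falls inside a stay, it could also discard genuine bleeds on initial parenteral treatment. That trade-off is open to debate.

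**Conclusion.** The point holds as a gap in a fixed definition. As written, a listed bleeding code in any position of a stay during time at risk is an event whether or not the bleed is new, and the one planned sensitivity analysis does not separate re-coded bleeds from true ones. The clearest case is a traumatic intracranial bleed coded again at a readmission on treatment. For the reportable SNDS analysis only this readmission route matters.

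The size is unknown. The illustration runs from negligible (0.4 extra events) to noticeable (2.2-4.4 extra on about 12), entirely on assumed values of c and q. The conclusion rests on the text of the definitions rather than on these figures. It warrants an added analysis and a stated limitation, with the main definition left as it is.

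**What to change.** Keep the current sensitive definition as the main analysis, and make two changes.

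1. Add to 9.7.6.2 a pre-specified new-event sensitivity analysis for both co-primary outcomes. It would not count a bleeding code when the same bleeding site was already coded in the 6-month baseline (or since birth for children under six months), or when the stay began before the index date. Report by exposure category how many main-analysis events the rule removes, subject to small-cell suppression.
2. In 9.9, name the risk that an earlier bleed is coded again, as is already done for recurrent VTE.

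Cost: prior bleeding codes must be added to the baseline extraction, since 9.3.2.1.1 does not list them. The history itself is already an inclusion requirement (9.2.3.1), and site groups already exist in 9.3.2.1.3 and Annex 3. The downside is that true re-bleeds at the same site, and new bleeds in a stay that began before the index date, drop out of the sensitivity analysis; they stay in the main one. In older children, a bleed coded only before the six-month window would still escape the rule.
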